- CFB in **HAM-A Total** Score at Week 14/EOS: The HAM-A consists of 14 items. Each item is rated/scored on a 5-point Likert scale, where 0 = Not present, 1 = Mild, 2 = Moderate, 3 = Severe, and 4 = Very severe. The HAM-A (SIGH-A) Total score is the sum of all 14 items ranging from 0 to 56, where ≤ 17 indicates "mild anxiety severity," 18 to 24 indicates "moderate anxiety severity," 25 to 30 indicates "moderate to severe anxiety severity," and ≥ 31 indicates "severe anxiety." A CFB in HAM-A Total score <0 represents a better outcome (reduction in depression symptoms).
- CFB in **GAD-7 Total** score by visit: The GAD-7 scale is a self-reported 7-item questionnaire for screening and measuring the severity of generalized anxiety disorder. The patient scores each item on 4-point Likert scale, where 0 = Not at all, 1 = Several days, 2 = Over half the days, and 3 = Nearly every day. The GAD-7 Total Score is the sum of all 7 items ranging from 0 to 21, where a total score of 0 to 4 = None/Minimal anxiety, 5 to 9 = Mild anxiety, 10 to 14 = Moderate anxiety, and ≥ 15 = Severe anxiety. A CFB in GAD-7 Total score <0 represents a better outcome (reduction in anxiety symptoms).

WPAI:SHP scales will be derived from these 6 questions:

Q1 = currently employed;

Q2 = hours missed due to specified problem;

Q3 = hours missed other reasons;

Q4 = hours actually worked;

Q5 = degree problem affected productivity while working; where 0 = “My ADHD symptoms had no effect on my work” and 10 = “My ADHD symptoms completely prevented me from working”

[figure not shown]
Q6 = degree problem affected regular activities, other than work at a job; where 0 = “My ADHD symptoms had no effect on my daily activities” and 10 = “My ADHD symptoms completely prevented me from doing my daily activities”

[figure not shown]
- CFB in **WPAI:SHP Absenteeism** percentage by visit: The WPAI:SHP questionnaire consists of 6 items that ask about the number of hours missed from work or regular activities due to the specific health problem, and the degree of impairment while working or performing regular activities. WPAI outcomes are expressed as impairment percentages. Percent work time missed due to problem (absenteeism) is calculated using the following formula: $[Q2/(Q2+Q4)] \times 100$ (range 0 to 100%). A higher percentage indicates greater impairment and less productivity. A CFB in percentage <0 represents a better outcome.

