- CFB in **WPAI:SHP Presenteeism** percentage by visit: Percent impairment while working due to problem (presenteeism) is calculated using the following formula: $[Q5/10] \times 100$ (range 0 to 100%). A higher percentage indicates greater impairment and less productivity. A CFB in percentage <0 represents a better outcome.
- CFB in **WPAI:SHP Work Productivity** percentage by visit: Percent overall work impairment due to problem is calculated using the following formula: $[Q2/(Q2+Q4) + ((1 - (Q2/(Q2+Q4))) \times (Q5/10))] \times 100$ (range 0 to 100%). A higher percentage indicates greater impairment and less productivity. A CFB in percentage <0 represents a better outcome.
- CFB in **WPAI:SHP Regular Activity** percentage by visit: Percent activity impairment due to problem is calculated using the following formula: $[Q6/10] \times 100$ (range 0 to 100%). A higher percentage indicates greater impairment and less productivity. A CFB in percentage <0 represents a better outcome.
- **The BRIEF-A** is a standardized 75-item self-rating scale that assesses overall functioning (GEC) and 9 non-overlapping scales among 2 summary index scales (Metacognition Index [MI] and Behavioral Regulation Index [BRI]) that assess aspects of executive function and problems with self-regulation from the perspective of the individual. Raw GEC scores, BRI, MI and their subscales (individual scales) will be converted to T-scores (T-score ≥ 65 is considered abnormally elevated) using Appendix A of the BRIEF-A Professional Manual and change from baseline in T-scores will be calculated. A lower change from baseline GEC T-score (<0) represents a better outcome.
- CFB in **BRIEF-A Global Executive Function (GEC) T-Score** at Week 14/EOS:
Behavioral Regulation Index [BRI]) that assess aspects of executive function and problems with self-regulation from the perspective of the individual. Subjects rate each

[figure not shown]
item on a 3-point scale (1=Never, 2=Sometimes, or 3=Often) based on their experience in past month. The sum of 70 items yields the GEC raw score (range: 70-210).

[figure not shown]
- CFB in the **BRIEF-A Behavioral Regulation Index (BRI)** T-score at Week 14/ EOS: The BRI captures the ability to maintain appropriate regulatory control of one's own behavior and emotional responses. The sum of 30 items yields the BRI raw score (range: 30-90).

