5.6. Handling of Missing data

5.6.1. Missing Efficacy Endpoints

Missing efficacy variables will be handled using the following rules:

- For AISRS Total Score and subscales Inattention & Hyperactivity/Impulsivity, if more than 3 items are missing then the total score will be set to missing. If ≤ 3 items are missing then the values for the missing items will be imputed using the mean of the non-missing items rounded to the nearest integer.
- For ASRSv1.1 Total Score and subscales Inattention & Hyperactivity/Impulsivity, if more than 3 items are missing then the total score will be set to missing. If ≤ 3 items are missing then the values for the missing items will be imputed using the mean of the non-missing items rounded to the nearest integer.

- For the following scales, if 1 of the individual item score is missing, either the total or subscale score will be set to missing. GAD-7 Total Score, HAM-A Total Score, BRIEF-A GEC Total Raw Score, BRIEF-A BRI Raw Score, BRIEF-A MI Raw Score, all the 9 non-overlapping BRIEF-A subscales.
- For WPAI:SHP, if Q1 = No, questions 2-5 are not applicable. If Q1 = Yes, questions 2 through 6 (Q2-Q6) are not allowed to be missing. If these questions are missing, then any scores calculated using the missing questions are also set to missing. For example, Absenteeism (hours) is derived from questions 2 and 4 (Q2 and Q4), if either Q2 or Q4 is missing, then Absenteeism will be set to missing. The same logic applies to the three-remaining score.
- For PSQI, questions 1 through 9 (Q1-Q9) are not allowed to be missing. If these questions are missing, then any scores calculated using missing questions are also set to missing. For example, “Sleep Latency” is derived based on Q2 and Q5a, if either Q2 or Q5a is missing, the “Sleep Latency” score will be set to missing, and the same logic applies to the other remaining scales. If a range is given for an answer (for example, ‘30 to 60’ is written as the answer to Q2, minutes to fall asleep), use the mean.

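### SAP 5.6.1 sets WPAI:SHP Work Productivity to missing when Q5 is blank, even where zero hours worked because of ADHD fixes the score at 100%

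*SAP*

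**What the plan says.** SAP 5.6.1 gives the missing-item rule for the WPAI:SHP. Its one not-applicable provision concerns participants without a job: "For WPAI:SHP, if Q1 = No, questions 2-5 are not applicable". For everyone else, "If Q1 = Yes, questions 2 through 6 (Q2-Q6) are not allowed to be missing". The consequence of a gap is that "If these questions are missing, then any scores calculated using the missing questions are also set to missing". The section works this through for Absenteeism (Q2 and Q4) and then adds: "The same logic applies to the three-remaining score". Zero hours worked is not mentioned.

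SAP 4.2 defines the items and scores. Q2 is introduced as "Q2 = hours missed due to specified problem", Q4 is the hours worked, and Q5 as "Q5 = degree problem affected productivity while working", rated from 0 to 10. The top anchor of Q5 says that symptoms wholly prevented working. Absenteeism is [Q2/(Q2+Q4)] × 100. Work Productivity is [Q2/(Q2+Q4) + (1 − Q2/(Q2+Q4)) × (Q5/10)] × 100, with a stated range of 0 to 100%.

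The change from baseline in Work Productivity by visit is a secondary endpoint (SAP 7.2). It is summarised descriptively in the Full Analysis Set, and a nominal p-value and confidence interval at Week 14/EOS are optional. No formal hypotheses are planned (SAP 5.5).

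**The concern.** Q5 asks about productivity during work. An employed participant who worked no hours because of ADHD might leave it blank. The missing-item rule then voids Work Productivity, because its formula contains Q5. Yet in exactly this case the formula does not depend on Q5, so the rule discards a value that the SAP has already fixed.

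Scores lost in this way are always at the ceiling, so the missingness is informative. At a treatment visit, a worst possible result drops out of the summary. At baseline, the participant loses every Work Productivity change score, including any recovery. Absenteeism keeps the same person at 100%, so the Absenteeism and Work Productivity summaries can rest on different participants. Two people with identical hours are also handled differently if one answers Q5 and the other does not.

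**Working it through.** **Inputs.** The Absenteeism and Work Productivity formulas are from SAP 4.2, and the missing-item rule is from SAP 5.6.1. The documents do not give the frequency of zero hours worked, the frequency of a blank Q5 or the mean score, so these are assumed below.

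**1. Stated range.** The Work Productivity formula was evaluated with Q2 and Q4 each from 0 to 60 hours (sum above 0) and Q5 from 0 to 10. The minimum is 0% and the maximum 100%, which reproduces the SAP's range.

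**2. Zero hours worked because of ADHD.** With Q4 = 0 and Q2 > 0, Q2/(Q2+Q4) = 1, so

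Work Productivity = [1 + (1 − 1) × Q5/10] × 100 = 100%.

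For Q2 = 1, 8, 20, 40 and 60 hours, every Q5 from 0 to 10 gave 100%. Absenteeism is also 100% in each case.

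**3. The SAP rule applied to that case.**

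| Q2 | Q4 | Q5 | Absenteeism | Work Productivity under the SAP |
|---|---|---|---|---|
| 40 | 0 | 10 | 100% | 100% |
| 40 | 0 | blank | 100% | missing |

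**4. Some hours worked.** With Q2 = 10 and Q4 = 30, a blank Q5 leaves the score anywhere from 25% (Q5 = 0) to 100% (Q5 = 10). The score cannot be determined, and setting it to missing is reasonable.

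**5. Size at one visit.** Among employed respondents, let f be the share with Q2 > 0 and Q4 = 0, p the chance that Q5 is blank for them, and m the mean of the scores that are kept. The full mean is f × p × 100 + (1 − f × p) × m, and the reported mean is m. The understatement is therefore f × p × (100 − m).

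| f | p | m | Understatement (percentage points) |
|---|---|---|---|
| any | 0 | any | 0 |
| 0.5% | 1 | 60% | 0.005 × 40 = 0.2 |
| 1% | 0.5 | 50% | 0.005 × 50 = 0.25 |
| 2% | 1 | 50% | 0.02 × 50 = 1.0 |
| 5% | 0.5 | 40% | 0.025 × 60 = 1.5 |
| 5% | 1 | 40% | 0.05 × 60 = 3.0 |

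**6. Change from baseline.** A lost Week 14 score of 100% removes a change of 100 minus baseline, which is zero or a worsening. A lost baseline of 100% removes changes of follow-up minus 100, which are zero or an improvement. The two act in opposite directions, and the documents give nothing from which to find the balance.

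**7. No hours of either kind.** With Q2 = Q4 = 0, as could happen during leave, both formulas are 0/0 and SAP 5.6.1 is silent.

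**The case against.** The strongest reply is that Q5 may never be blank here. Its top anchor fits a participant whom ADHD kept from all work, and with that answer, or any other, the SAP as written already returns 100%. The questionnaire is completed in the study app, the SAP says the items may not be missing, and Protocol 11.4 plans programmed checks for complete entry. These point towards an answered Q5, but they do not settle it: neither document describes a skip pattern or says that the app enforces a response. This reply stands to the extent that the loss is conditional and its lower bound is zero.

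A reader might infer that the rule deletes participants. It does not. Membership of the Full Analysis Set depends only on the AISRS (SAP 5.3), and Absenteeism and Regular Activity are still scored. A reader might also infer that the rule removes only worst-case values. It applies to every blank Q5 among employed participants, and step 4 shows that it is right when some hours were worked.

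It is also fair to say that this is one of many descriptive secondary endpoints, and no conclusion has been shown to change. The 0/0 case is missing detail, since an undefined ratio gives no score in any event.

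**Conclusion.** The defect holds in a narrow form. For an employed participant with Q2 > 0, Q4 = 0 and Q5 blank, SAP 5.6.1 sets Work Productivity to missing although the SAP 4.2 formula gives 100%. What is lost is that visit's Work Productivity score, or all of the participant's Work Productivity change scores if the visit is baseline.

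Over the assumed ranges (f from 0.5% to 5%, p from 0 to 1, m from 40% to 60%), the visit mean is understated by 0 to 3.0 percentage points. The upper end needs f = 5%, every such Q5 blank and m = 40%. A reader might infer that the endpoint is certainly biased in the drug's favour. The documents do not support this: they do not show that Q5 is left blank, and for change from baseline the net direction is unknown. The effect is probably small, but the correction is exact.

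**What to change.** Add to the WPAI:SHP rule in SAP 5.6.1: *If Q1 = Yes, Q2 > 0 and Q4 = 0, Work Productivity = 100% whether or not Q5 is answered.* Where Q5 is answered this changes nothing, because the formula already gives 100%. The general rule for a blank Q5 stays in place when Q4 > 0.

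As a clarification only, state that Absenteeism and Work Productivity are not calculable when Q2 = Q4 = 0.

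The point requires no change to the app and no exclusion of entered Q5 answers from Presenteeism. The cost is one sentence, one clarifying line and a few lines of programming, ideally before database lock. No extra data are needed.

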#### 9.2.2.6 Pittsburgh Sleep Quality Index (PSQI)

The Pittsburgh Sleep Quality Index (PSQI) is a validated and effective instrument used to measure the quality and patterns of sleep in adults ([Buysse et al., 1989](#)). The PSQI is a self-rated questionnaire which assesses sleep quality and disturbances over a 1-month time interval. It is a 19-item questionnaire out of which generate 7 component scores (or domains): subjective sleep quality, sleep latency, sleep duration, habitual sleep efficiency, sleep disturbances, use of sleep medication, and daytime dysfunction over the last month. The individual rates each of these seven areas of sleep. Scoring of the answers is based on a 0 to 3 scale, whereby 3 reflects the negative extreme on the Likert Scale. A global sum of "5" or greater indicates a "poor" sleeper. Although there are several questions that request the evaluation of the client's bedmate or roommate, these are not scored, nor reflected in the attached instrument. An updated scoring was established from original scoring algorithm: *if*

	Protocol 812P413	
	Page 41 of 61	Version 2.0

5J is not complete or the value is missing, it now counts as a "0". It takes 10-15 minutes to complete the PSQI. The PSQI is being used in this study to assess self-reported sleep behavior and daytime function during Qelbree treatment in adults with ADHD. The PSQI global [REDACTED] scores are secondary outcome measures for this study.

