- CFB in the **BRIEF-A Metacognitive Index (MI)** T-score at Week 14/ EOS: MI reflects individual's ability to problem solve (includes initiate activity, generate ideas, sustain working memory, plan/organize approaches, monitor success/failure, and organize materials/environment). The sum of 40 items (list can be found in the BRIEF-A manual) yields the MI raw score (range: 40-120).
- CFB in **PSQI Global** score at Week 14/EOS: The PSQI is a 19-item questionnaire that generates a Global score out of which generate 7 component scores (or domains): subjective sleep quality, sleep latency, sleep duration, habitual sleep efficiency, sleep disturbances, use of sleep medication, and daytime dysfunction over the last month. The individual rates each of these 7 areas of sleep. Scoring of the answers is based on a 0 to 3 scale, where a score of 3 reflects the negative extreme on the Likert Scale and 0 better on the individual scales. The sum of all the 7 components scores yields the global score (range 0-21); a global sum of "5" or greater indicates a "poor" sleeper.

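### The SAP's missing-item rule for the PSQI has no exception for item 5J, which the protocol scores as 0 when blank, so participants the protocol treats as scorable can drop out of the PSQI change endpoint

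*SAP*

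**What the plan says.** Protocol 9.2.2.6 describes the PSQI scoring and includes a specific rule for one sub-item. It reports that "An updated scoring was established from original scoring algorithm" and gives the change: if "5J is not complete or the value is missing, it now counts as a" zero. The same section names the PSQI global score as a secondary outcome.

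SAP 5.6.1 handles blank PSQI items as follows: "For PSQI, questions 1 through 9 (Q1-Q9) are not allowed to be missing", and "If these questions are missing, then any scores calculated using missing questions are also set to missing". Its worked example is sleep latency, which "is derived based on Q2 and Q5a, if either Q2 or Q5a is missing" goes to missing; it then adds that "the same logic applies to the other remaining scales". Item 5J is not mentioned.

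SAP 4.2 defines the global score: "The sum of all the 7 components scores yields the global score", with range 0 to 21. That section follows the protocol's PSQI description closely but does not carry over the sentence on 5J.

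SAP 7.2 lists the endpoint as the change from baseline in the global score at Week 14/EOS. The schedules (Protocol Table 1, SAP Table 2) show the PSQI at Televisit 1b and Week 14/EOS only. SAP section 9 states that nothing differs from the analyses planned in the protocol.

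**The concern.** The two documents give different results for the same questionnaire. Someone who answers everything except 5J has a global score under the protocol and none under the SAP as written. A programmer working from SAP 5.6.1 alone would code the SAP's result, and SAP section 9 gives no hint that a departure was made.

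At stake is the number of participants who contribute to the sleep endpoint. It is a change score from two assessments, so a blank 5J at either one is enough to lose the person, and no intermediate visit can stand in. SAP 5.6.1 fills in up to three missing items for the AISRS and ASRSv1.1-SC but has no such provision for the PSQI, so nothing recovers the record. Sleep also matters for this drug: Protocol 3.2.2 reports insomnia in 23% of treated adults against 7% on placebo in the earlier controlled trial.

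**Working it through.** **Does the SAP rule reach 5J?** The rule covers Q1 to Q9, and its own example is the sub-item Q5a. It therefore operates at sub-item level within Q5, and 5J falls inside it. The bullet just before it, on the WPAI:SHP, writes out an exception for participants who are not employed. The PSQI bullet writes none.

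**Consequence for one participant with only 5J blank.**

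| Step | Protocol 9.2.2.6 | SAP 5.6.1 as written |
|---|---|---|
| Value of 5J | 0 | missing |
| Component that uses 5J | formed | missing |
| Components that do not use 5J | formed | formed |
| Global score (sum of 7) | formed | missing |
| Change from baseline | formed if the other visit is scorable | missing |

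The documents do not say which component uses 5J. That does not matter here: a rule that gives 5J a score implies that it enters one, and a single missing component is enough to leave the sum undefined.

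**The plan's own figure.** Protocol 12.3 plans up to 750 dosed and up to 500 completers at 33% attrition. Check: 750 × (1 − 0.33) = 502.5, and 500 / (1 − 0.33) = 746.3, rounded up to 747. The figures agree. The conflict does not rest on them; 500 serves only as a base for the illustration.

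**Size of the loss.** Let p be the share leaving 5J blank at each of the two assessments, taken as equal. The documents give no value, so p is an assumption.

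- If the same people leave it blank both times, the share lost is p.
- If blanks at the two times are independent, the share lost is 1 − (1 − p)².

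| Assumed p | Same people: 500 × p | Independent: 500 × [1 − (1 − p)²] |
|---|---|---|
| 0 | 0 | 0 |
| 1% | 5 | 500 × 0.0199 = 9.95, about 10 |
| 5% | 25 | 500 × 0.0975 = 48.75, about 49 |
| 10% | 50 | 500 × 0.19 = 95 |

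These two cases bound the loss as long as skipping the item once does not make skipping it again less likely. Under the protocol's rule the loss for this reason is zero at every p.

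**The case against.** The best defence is that the two rules can be read together. The protocol assigns a blank 5J the value 0, so it is no longer missing when SAP 5.6.1 is applied, and a rule for one item normally governs over a general one. The protocol sentence also sits in an instrument description, not in the statistical section, and Protocol 12.1 leaves details to the SAP. This reading is probably what the sponsor would want, but the SAP does not state it. The SAP rule is complete as worded, reaches Q5 sub-items and names no exception. What stands is that SAP section 9 need not be read as a false declaration. This looks like an omission.

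A second defence is that some text is withheld: a gap follows the mention of the PSQI global score in Protocol 9.2.2.6, and SAP 4.3 appears without content. A 5J rule could sit there, and its absence from withheld text is not counted against the plan. The visible rule in 5.6.1 still conflicts with the visible rule in the protocol.

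A third defence is that the PSQI is completed in the study app and Protocol 11.4 promises programmed checks for complete entry. If the app requires an answer to 5J, nobody is lost. The documents do not say whether it does, and both documents provide for blank PSQI answers. This point stands as a reason why the loss may be zero.

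A reader might infer that the loss is selective: those with nothing to report skip 5J, so the analysed group tilts toward worse sleepers. The documents do not support this. They do not say what 5J asks, and a tilt in the level of sleep quality would not by itself show a bias in change from baseline.

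**Conclusion.** The conflict is real on the text: for a questionnaire complete except for 5J, the protocol gives a global score and the SAP does not. It concerns 5J only; the protocol states no competing rule for other blank items in Q1 to Q9.

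The size is unknown. It runs from none, if answers are forced, to roughly 50 to 95 of 500 completers at an assumed 10% blank rate. A reader might go further and assume much higher rates with independent visits (50% blank would give 1 − 0.5² = 75% lost). Nothing in the documents supports such rates or independence between visits.

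Nor does the point threaten the trial's main conclusions. The primary AISRS analysis and the safety analyses are untouched, and PSQI components that do not use 5J survive. The study has no formal hypotheses and no power basis, and SAP 7.2 offers a nominal p-value for secondary endpoints only as an optional exploration. Severity is minor to moderate: worth settling before the data are analysed, because choosing between the two rules afterwards would be post hoc.

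**What to change.** Add to the PSQI bullet in SAP 5.6.1: *If item 5J is blank or incomplete it is scored 0 (protocol 9.2.2.6); the missing rule applies to the remaining Q1-Q9 items.* Apply it at both assessments. If the sponsor does intend to leave such questionnaires unscored, SAP section 9 should say so and give the reason.

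The cost is one sentence in the SAP and one line of derivation code. No data collection changes.
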